## 11.0 DATA SUBMISSION SCHEDULE

Case report forms with appropriate source documentation will be completed according to the schedule listed in this section.

Case Report Form	Submission Schedule
Original Consent Form	Prior to registration
On-Study Form	Prior to starting treatment
Surgery Form	Time of surgery
Treatment Form	At completion of RT End of every cycle during adjuvant TMZ
Correlatives Form	Time of surgery Time of progression
Toxicity Form	Continuous
Treatment Summary Form	Completion of treatment
Follow Up Form	2 years after last dose of disulfiram
MedWatch Form	See Section 7.0 for reporting requirements

## 12.0 MEASUREMENT OF EFFECT

### 12.1 Antitumor Effect – Solid Tumors

For the purposes of this study, patients should be re-evaluated for response every 9 +/- 1 weeks. In addition to a baseline scan, confirmatory scans should also be obtained 9 weeks (not less than 4) weeks following initial documentation of objective response.

Response and progression will be evaluated in this study using the updated response assessment criteria for high-grade gliomas: Response Assessment in Neuro-Oncology (RANO) working group guideline [78].

Criteria for Determining First Progression Depending on Time from Initial Chemoradiotherapy

First Progression	Definition
Progressive disease < 12 weeks after completion of chemoradiotherapy	Progression can only be defined using diagnostic imaging if there is new enhancement outside of the radiation field (beyond the high-dose region or 80% isodose line) or if there is unequivocal evidence of viable tumor on histopathologic sampling (eg, solid tumor areas [ie, > 70% tumor cell nuclei in areas], high or progressive increase in MIB-1 proliferation index compared with prior biopsy, or evidence for histologic progression or increased anaplasia in tumor). Note: Given the difficulty of differentiating true progression from pseudoprogression, clinical decline alone, in the absence of radiographic or histologic confirmation of progression, will not be sufficient for definition of progressive disease in the first 12 weeks after completion of concurrent chemoradiotherapy.
Progressive disease ≥ 12 weeks after chemoradiotherapy completion	
 
1. New contrast-enhancing lesion outside of radiation field on decreasing, stable, or increasing doses of corticosteroids.
 
2. Increase by ≥ 25% in the sum of the products of perpendicular diameters between the first postradiotherapy scan, or a subsequent scan with smaller tumor size, and the scan at 12 weeks or later on stable or increasing doses of corticosteroids.
 
3. Clinical deterioration not attributable to concurrent medication or comorbid conditions is sufficient to declare progression on current treatment but not for entry onto a clinical trial for recurrence.
 
4. For patients receiving antiangiogenic therapy, significant increase in T2/FLAIR nonenhancing lesion may also be considered progressive disease. The increased T2/FLAIR must have occurred with the patient on stable or increasing doses of corticosteroids compared with baseline scan or best response after initiation of therapy and not be a result of comorbid events (eg, effects of radiation therapy, demyelination, ischemic injury, infection, seizures, postoperative changes, or other treatment effects).
 

Criteria for Response Assessment Incorporating MRI and Clinical Factors (Adapted from JCO 2010)

Response	Criteria
Complete response	
 
• Requires all of the following: complete disappearance of all enhancing measurable and nonmeasurable disease sustained for at least 4 weeks.
 
• No new lesions; stable or improved nonenhancing (T2/FLAIR) lesions.
 
• Patients must be off corticosteroids (or on physiologic replacement doses only) and stable or improved clinically. Note: Patients with nonmeasurable disease only cannot have a complete response; the best response possible is stable disease.
 

Partial response	
 
Requires all of the following: 
 
• ≥ 50% decrease compared with baseline in the sum of products of perpendicular diameters of all measurable enhancing lesions sustained for at least 4 weeks.
 
• No progression of nonmeasurable disease.
 
 
 

Response	Criteria
	
 
Stable or improved nonenhancing (T2/FLAIR) lesions on same or lower dose of corticosteroids compared with baseline scan; the corticosteroid dose at the time of the scan evaluation should be no greater than the dose at time of baseline scan.
 
Stable or improved clinically. Note: Patients with nonmeasurable disease only cannot have a partial response; the best response possible is stable disease.
 

Stable disease	
Requires all of the following:
 
 
Does not qualify for complete response, partial response, or progression.
 
Stable nonenhancing (T2/FLAIR) lesions on same or lower dose of corticosteroids compared with baseline scan. In the event that the corticosteroid dose was increased for new symptoms and signs without confirmation of disease progression on neuroimaging, and subsequent follow-up imaging shows that this increase in corticosteroids was required because of disease progression, the last scan considered to show stable disease will be the scan obtained when the corticosteroid dose was equivalent to the baseline dose.
 

Progression	
Defined by any of the following:
 
 
<math>\geq 25\%</math> increase in sum of the products of perpendicular diameters of enhancing lesions compared with the smallest tumor measurement obtained either at baseline (if no decrease) or best response, on stable or increasing doses of corticosteroids*. The absolute increase in any dimension must be at least 5mm when calculating the products.
 
Significant increase in T2/FLAIR nonenhancing lesion on stable or increasing doses of corticosteroids compared with baseline scan or best response after initiation of therapy* not caused by comorbid events (e.g. radiation therapy, demyelination, ischemic injury, infection, seizures, postoperative changes, or other treatment effects).
 
Any new measurable lesion.
 
Clear clinical deterioration not attributable to other causes apart from the tumor (e.g. seizures, medication adverse effects, complications of therapy, cerebrovascular events, infection, and so on) or changes in corticosteroid dose.
 
Failure to return for evaluation as a result of death or deteriorating condition; or clear progression of nonmeasurable disease.
 

- NOTE. All measurable and nonmeasurable lesions must be assessed using the same techniques as at baseline.
- Abbreviations: MRI, magnetic resonance imaging; FLAIR, fluid-attenuated inversion recovery.
- Stable doses of corticosteroids include patients not on corticosteroids.

## 12.2 Disease Parameters

**Measurable disease:** Bi-dimensionally measurable lesions with clearly defined margins by MRI scan. All tumor measurements must be recorded in millimeters (or decimal fractions of centimeters).

**Non-measurable or evaluable disease:** Uni-dimensionally measurable lesions or lesions with margins not clearly defined such as areas of T2/FLAIR signal abnormality or poorly defined enhancing abnormality.

**Note:** For cystic lesions, the only measurable part is any enhancement area around the cyst that is clearly defined and bi-dimensionally measurable. The cyst itself should not be considered measurable or non-measurable disease.

**Target lesions:** All measurable lesions that are residual of the lesion treated with MLA should be identified as target lesions and recorded and measured. Target lesions should be selected on the basis of their size (lesions with the longest diameter), but in addition should be those that lend themselves to reproducible repeated measurements. It may be the case that, on occasion, the largest lesion does not lend itself to reproducible measurement in which circumstance the next largest lesion, which can be measured reproducibly should be selected. When there are too many measurable lesions, choose the largest 3 lesions as target lesions to follow. The other measurable lesions should be considered evaluable for the purpose of objective status determination.

**Non-target lesions:** All non-measurable lesions should be identified as non-target lesions and should also be recorded at baseline. Measurements of these lesions are not required, but the presence, absence, or in rare cases unequivocal progression of each should be noted throughout follow-up.

### **12.3 Methods for Evaluation of Measurable Disease**

All measurements should be taken and recorded in metric notation using a ruler. All baseline evaluations should be performed as closely as possible to the beginning of treatment and never more than 2 weeks before the beginning of the treatment.

**Clinical lesions:** Clinical lesions will only be considered measurable on brain MRI when they are  $\geq 5$  mm diameter as assessed using a ruler.

**Histology:** This technique can be used to differentiate between partial responses (PR) and complete responses (CR) in rare cases when biopsy or surgical resection of a measurable lesion is clinically indicated.

**Perfusion/CBV:** This advanced brain MRI technique can be used as an adjunct test to determine treatment response or disease status. However, it should not be used as the primary or sole method to determine response or disease status.

**Brain FDG-PET coupled with head CT or brain MRI:** This advanced metabolic imaging technique can be used as an adjunct test to determine response or disease status. However it should be used as the primary or sole method of determining response or disease status.

#### **12.3.1 Evaluation of Target Lesions**

**Complete Response (CR):** Disappearance of all target lesions.

**Partial Response (PR):**  $\geq 50\%$  decrease compared with baseline in the sum of

products of perpendicular diameters of all target lesions sustained for at least 4 weeks.

**Progressive Disease (PD):** At least a 25% increase in the sum of products of perpendicular diameters of at least 1 target lesion, taking as reference the smallest sum of products of perpendicular diameters on study (this includes the baseline sum if that is the smallest on study). The absolute increase in any dimension must be at least 5mm when calculating the products of perpendicular diameters.

**Stable Disease (SD):** Neither sufficient shrinkage to qualify for PR nor sufficient increase to qualify for PD, taking as reference the smallest sum of products of perpendicular diameters while on study.

### **12.3.2 Evaluation of Non-Target Lesions**

**Complete Response (CR):** Disappearance of all non-target lesions.

**Non-CR/Non-PD:** Persistence of one or more non-target lesion(s).

**Progressive Disease (PD):** Appearance of one or more new lesions and/or unequivocal progression of existing non-target lesions on stable or increasing doses of corticosteroids compared with baseline scan or best response after initiation of therapy\* not caused by comorbid events (e.g. radiation therapy, demyelination, ischemic injury, infection, seizures, postoperative changes, or other treatment effects). Unequivocal progression should not normally trump target lesion status. It must be representative of overall disease status change, not a single lesion increase.

Although a clear progression of “non-target” lesions only is exceptional, the opinion of the treating physician should prevail in such circumstances, and the progression status should be confirmed at a later time by the review panel (or Principal Investigator).

### **12.3.3 Evaluation of Best Overall Response**

The best overall response is the best response recorded from the start of the treatment until disease progression/recurrence (taking as reference for progressive disease the smallest measurements recorded since the treatment started). The patient's best response assignment will depend on the achievement of both measurement and confirmation criteria.

### Summary of the RANO Response Criteria (Adapted from JCO 2010)

Criterion	CR	PR	SD	PD
T1 gadolinium enhancing disease	None	$\geq 50\% \downarrow$	$< 50\% \downarrow$ but $< 25\% \uparrow$	$\geq 25\% \uparrow^*$
T2/FLAIR	Stable or $\downarrow$	Stable or $\downarrow$	Stable or $\downarrow$	$\uparrow^*$
New lesion	None	None	None	Present*
Corticosteroids	None	Stable or $\downarrow$	Stable or $\downarrow$	NA†
Clinical status	Stable or $\uparrow$	Stable or $\uparrow$	Stable or $\uparrow$	$\downarrow^*$
Requirement for response	All	All	All	Any*

Abbreviations: RANO, Response Assessment in Neuro-Oncology; CR, complete response; PR, partial response; SD, stable disease; PD, progressive disease; FLAIR, fluid-attenuated inversion recovery; NA, not applicable.

\* Progression occurs when this criterion is present.

† Increase in corticosteroids alone will not be taken into account in determining progression in the absence of persistent clinical deterioration.

NOTE: Patients may continue on treatment and remain under close observation and evaluation at 4-8 week intervals if there is uncertainty regarding whether pseudoprogression may be present as determined by the investigators. If subsequent radiographic or clinical assessments suggest that the patient is in fact experiencing progression, then the date of progression should be the time point at which this issue was first raised. Similarly, stable disease may be assigned in cases of presumed “pseudoprogression” associated with decreased steroid use.

#### 12.3.4 Duration of Response

**Duration of overall response:** The duration of overall response is measured from the time measurement criteria are met for CR or PR (whichever is first recorded) until the first date that recurrent or progressive disease is objectively documented (taking as reference for progressive disease the smallest measurements recorded since the treatment started).

The duration of overall CR is measured from the time measurement criteria are first met for CR until the first date that progressive disease is objectively documented.

**Duration of stable disease:** Stable disease is measured from the start of the treatment until the criteria for progression are met, taking as reference the smallest measurements recorded since the treatment started, including the baseline measurements.

#### 12.3.5 Progression-Free Survival

PFS is defined as the duration of time from start of treatment to time of progression or death, whichever occurs first.

## 13.0 DATA AND SAFETY MONITORING

In compliance with the Washington University Institutional Data and Safety Monitoring Plan, the Principal Investigator will provide a Data and Safety Monitoring (DSM) report to the Washington University Quality Assurance and Safety Monitoring Committee (QASMC) semi-annually beginning six months after accrual has opened (if at least five patients have been enrolled) or one year after accrual has opened (if fewer than five patients have been enrolled at the six-month mark).

During the phase I dose escalation, the Principal Investigator will review all patient data at least monthly (or before each dose-escalation if occurring sooner than monthly), and provide a semi-annual report to the Quality Assurance and Safety Monitoring Committee (QASMC). During the phase II, the Principal Investigator will review all patient data at least every six months, and provide a semi-annual report to the QASMC. This report will include:

- HRPO protocol number, protocol title, Principal Investigator name, data coordinator name, regulatory coordinator name, and statistician
- Date of initial HRPO approval, date of most recent consent HRPO approval/revision, date of HRPO expiration, date of most recent QA audit, study status, and phase of study
- History of study including summary of substantive amendments; summary of accrual suspensions including start/stop dates and reason; and summary of protocol exceptions, error, or breach of confidentiality including start/stop dates and reason
- Study-wide target accrual and study-wide actual accrual
- Protocol activation date
- Average rate of accrual observed in year 1, year 2, and subsequent years
- Expected accrual end date and accrual by cohort
- Objectives of protocol with supporting data and list the number of participants who have met each objective
- Measures of efficacy
- Early stopping rules with supporting data and list the number of participants who have met the early stopping rules
- Summary of toxicities separated by cohorts with the number of dose-limiting toxicities indicated
- Abstract submissions/publications
- Summary of any recent literature that may affect the safety or ethics of the study

The study principal investigator and Research Patient Coordinator will monitor for serious toxicities on an ongoing basis. Once the principal investigator or Research Patient Coordinator becomes aware of an adverse event, the AE will be reported to the HRPO and QASM Committee according to institutional guidelines.

## 14.0 STATISTICAL CONSIDERATIONS

### 14.1 Definition of Primary Endpoint

The maximum tolerated dose (MTD) of DSF with concurrent RT+TMZ will be defined as the dose associated with a 20% probability of dose-limiting toxicity (DLT). Toxicity will be coded using CTCAE version 4.0, and DLT will be defined as toxicity that occurs within 18 weeks from the first day of RT and is possibly, probably or definitely related to DSF/Cu (or 12 weeks from the completion of RT if there is a delay/interruption of RT).

For the expansion cohort of GBM with *IDH*, *BRAF*, and *NF1* mutations, the overall survival (OS) of this molecularly-defined cohort will be measured from the first day of RT.

### 14.2 Definition of Secondary and Exploratory Endpoints

1. The adverse events will be graded by NCI CTCAE version 4.0.
2. Progression-free survival (PFS) will be determined from the first day of RT to the time of tumor progression or death, whichever occurs first. Tumor progression will be determined using the RANO criteria.
3. Intratumor and plasma concentration of DSF metabolite (ditiocarb-copper complex) will be determined using mass spectrometer method.
4. Pharmacodynamics studies on glutamate metabolism will include measurement of glutamine, glutamate, aspartate, glucose, and lactate levels in blood and tumor tissues using mass spectrometry method.
5. Pseudo-progression is defined as a transient increase of tumor after chemoradiotherapy that subsequently stabilizes without a change of therapy.

### 14.3 Analytic Plan for Primary Endpoint

#### 14.3.1 Background of Time-to-Event Continual Reassessment Method (TITE-CRM) and Trial Rules

The standard phase I 3+3 design is poorly suited for trials of RT, for which toxicities may occur up to several months after treatment. In this case, the 3+3 design, or any design that requires all patients to have completed observation for toxicity, is subject to openings and closings as patients present after a dose level potentially has filled, but before sufficient time has elapsed to be certain that treatment has not produced DLT.

As such, dose escalation for this trial will be guided by the Time-to-Event Continual Reassessment Method (TITE-CRM). TITE-CRM seeks to determine the target dose, defined as the dose most closely identified with the target rate, which is the largest acceptable probability of toxicity, determined a priori by the investigators based on the relative costs and benefits of the treatment (typically between 5% and 25%). As the trial progresses and patients do or do not experience toxicities at different doses, the estimates of probability of toxicity are recalculated using a

Bayesian expectation, and subsequent patients are assigned to doses under the principle to always treat at the target dose. In a Monte Carlo simulation of 60,000 phase I trials comparing 3+3 design to TITE-CRM in studies with delayed toxicity, the TITE-CRM trials were significantly shorter when toxicity observation times are long, treated more patients at or above the MTD, identified the MTD more accurately, but did not expose patients to significant additional risk [79]. Additionally, given that TITE-CRM concentrates most of the accrual around the MTD, early estimates of efficacy are possible for a phase I trial.

The Time-to-Event Continual Reassessment Method (TITE-CRM) proposed by Cheung and Chappell is an adaptive Phase I design [80]. In a TITE-CRM clinical trial, patients enroll as they become available to be studied. Each participant is assigned to a dose level from a set of dose levels pre-defined by investigators and is monitored for DLTs over time. The design is adaptive in that the dose level assigned to a newly enrolled patient depends on the dose level assignments and DLT outcomes of the patients already in the study. A patient's observation period ends at the occurrence of a DLT, or if a DLT does not occur, after a fixed time T of follow-up. The trial ends when a fixed number of patients,  $n$ , have been observed. Once the final patient has been observed, the MTD can be estimated using the available data. The TITE-CRM differs from the traditional CRM in that the estimation process is weighted to account for the proportion of the observation period that each currently enrolled patient has been observed. By not requiring complete observation before the enrollment of the next patient, new participants can be assigned a dose and begin evaluation as they become available, subsequently shortening the overall duration of the study.

The Biostatistics Unit at the University of Michigan Comprehensive Cancer Center has developed a program `titecrm.sas` for SAS 9 (SAS Institute, Inc.; Cary, NC) that makes all of the calculations necessary to determine dose allocation of a trial in real-time. They have also developed simulation programs that allow the user to determine the efficacy of the trial based on *a priori* estimates of the probabilities of toxicity and necessary sample sizes.

In order to properly utilize this type of trial, a few assumptions and many rules must be determined before the start of the trial. The main assumption that must be determined is how many different dose levels will be included in the trial and *a priori* estimates of the probability of a DLT at each of those dose levels. For this trial, we have 4 dose levels ( $d_1, \dots, d_4$ ) ranging from 125mg PO daily to 500 mg PO daily, with initial toxicity probability estimates ( $p_1, \dots, p_4$ ) ranging from 0.05 to 0.30, respectively. The following table shows the dose design with associated estimated probabilities of toxicity.

Dose Escalation Schedule		
Dose Level	Dose of DSF	Initial Toxicity Estimate
Level 1	125 mg PO daily	0.05
Level 2	250 mg PO daily	0.10
Level 3	375 mg PO daily	0.20
Level 4	500 mg PO daily	0.30

#### 14.3.2 TITE-CRM Design for the Dose-escalation Phase

The starting dose can have a large impact on the properties of the design. After the trial is completed, most information about the MTD will be obtained if many patients are treated at or near the MTD, thus the sooner the choice of dose can converge on the MTD the more effective the trial will be. However, with concerns about safety we will start at the one dose level lower than the expected MTD. Therefore, our starting dose for this trial will be 250 mg PO daily.

The next thing to be considered is the dose escalation rules. For this trial, we will only allow a single dose level escalation per new patient enrolled on the trial. Therefore, if the previous patient was treated at dose level,  $d_k$ , then a new patient can only be treated at dose levels  $d_{k+1}$  or lower. In order to determine at which level to treat the new patient, we will use a non-weighted, cumulative time of exposure approach. The total length of follow-up for DLT for any patient is 18 weeks. In order to efficiently and effectively determine the MTD, we allow for a dose change when the cumulative time of exposure is 18 weeks. Also, since previously published data shows that toxic events occur evenly throughout the time of the study we will not implement a weighting function. The dose for the next patient is selected so that the estimated probability at that dose is close to the target level. A feature of the dose escalation part of the TITE-CRM program is the flexibility in specifying the margin for the dose selection. This allows the selection of the dose level for the next patient that may have an estimated probability of toxicity larger than the target level but less than the target level plus the margin. It finds the dose closest to the target probability even if it has a higher estimated probability. For this trial we set the admissible margin to be 5%, therefore, the MTD will be chosen as the dose that yields a posterior toxicity estimate closest to 20% while being between 15% and 25%. The admissible margin is also used to help determine stopping rules for the trial. In order to account for the possibility of poor initial outcomes we will employ a run-in of 6 patients, meaning that the minimum number of treated patients will be 6. If after these 6 patients, or any other time during the trial, the lowest dose level has a posterior probability higher than 25% then the trial will stop.

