As for the rationale for the proposed expansion cohort, this is based on the promising finding of the dose-escalation phase of the study. After enrollment of the 18 patients for the dose-escalation phase, 8 patients were treated with DSF of 250 mg/day (dose level 2) and 10 patients with 375 mg/day (dose level 3). Three dose-limiting toxicities (DLTs) were observed: 1 with 250 mg/day (grade 2 urinary incontinence and ataxia), and 2 with 375 mg/day (both grade 3 elevated liver enzymes). The TITE-CRM model estimated the DLT probability of DSF to be 10% (95% CI: 3-29%) at 250 mg/day, and 21% (95% CI: 7-42%) at 375 mg/day. Thus, we have declared that the MTD of DSF in combination with RT/TMZ/Cu for GBM is 375 mg/day, and the recommended phase II dose is 250 mg/day. Furthermore, tumor mutations were evaluated with next-generation sequencing for all patients to explore possible biomarkers for response. Notably, GBM patients with *IDH* (n = 6), *BRAF* (n = 2), and *NF1* (n = 1) mutations exhibited much better PFS and OS than those without these mutations (n = 9): 1-year PFS of 100% vs 22%, respectively, p = 0.001; 1-year OS of 100% vs 42%, respectively, p = 0.006. Given that the historical PFS and OS of newly diagnosed GBM patients treated with RT and TMZ is approximately 27% and 60% at one year [4], respectively, the preliminary data of this molecular subset of GBM are thought-provoking and raise the possibility that these mutations make GBM tumors more sensitive to DSF/Cu in combination with chemoradiotherapy. Interestingly, all three mutations, which affect approximately 15-20% of GBM tumors, make tumor cells more dependent on glutamate for cellular metabolism [68-70]. As DSF metabolite can affect glutamate uptake, this may be the biological mechanism for the improved outcomes for GBM with these mutations. Thus, we have proposed to add an expansion cohort to this phase I/II study to treat additional GBM patients with *IDH*, *BRAF*, or *NF1* mutations to increase the statistical power of our preliminary finding.

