#### **14.3.4 Workflow**

The first patient will be enrolled on the trial and treated at the 250 mg PO daily dose level, which is one dose level below the hypothesized MTD. That patient will be entered into the titecrm.sas program and follow-up will begin from start of treatment (RT+TMZ+DSF+Cu). Although the entire study duration is 34 weeks or at the completion of adjuvant DSF, for the purposes of DLT evaluation, the patient will be followed from start of treatment until the patient completes 18 weeks of follow-up, has a DLT, or is lost to follow-up. If any of these endpoints occur, the statistician will be notified and the date corresponding to the event will be entered into the program. While there is a maximum follow-up of 18 weeks for observation of possible DLTs, sometimes patients have a delay in their treatment resulting in the need for a prolonged observation period (at least 12 weeks after completion of RT if there is delay/interruption of RT). This delay will be accounted for as needed for this study to ensure completed 18 week follow-up. When a new patient is enrolled on the trial the statistician will be notified of the date of enrollment. At this time the statistician will update the follow-up for all patients currently on the trial and determine the dose that will be administered for the new patient. We will utilize the cumulative time of exposure method which will allow the contribution of patients with no DLT at this time to be partially weighted consistent with their time observed. At this point, the program provides a summary of the number of patients treated at each dose so far, along with the number of DLTs that have occurred. The posterior probability and 95% credible intervals of dose limiting toxicity for each dose level is calculated. At this point, the model determines the dose level that has an estimated toxicity rate closest to 20% within the 5% admissible margin. The newly enrolled patient will be enrolled in the corresponding dose level if that dose level is within one dose jump from the dose level the most current patient is enrolled on. If the suggested dose level is more than one dose level from the current dose level, the next patient will be enrolled on the dose level that is closest to the current level in the direction of the dose level determined from the estimated posterior probability. This continues until the trial has accrued all 18 patients or, if after 6 patients are enrolled, the estimated posterior probability for the lowest dose level is higher than 25%.

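### No toxicity stopping rule is stated for the 15 expansion patients at 250 mg; the plan's only numeric rule is written for the escalation phase and read at 125 mg

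*Combined protocol and SAP*

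**What the plan says.** - Section 14.3.2, headed "TITE-CRM Design for the Dose-escalation Phase", sets a run-in of six patients. After that, or at any other point, if "the lowest dose level has a posterior probability higher than 25% then the trial will stop". Section 14.3.4 repeats the rule inside the enrolment workflow and says where that workflow ends: "This continues until the trial has accrued all 18 patients", or earlier if the rule is met.
- Section 14.3.1 gives four levels (125, 250, 375 and 500 mg) with initial DLT estimates of 0.05, 0.10, 0.20 and 0.30. The lowest level is therefore 125 mg.
- Section 1.3 reports 8 escalation patients at 250 mg (1 DLT) and 10 at 375 mg (2 DLTs), hence none at 125 mg. The model estimate was "10% (95% CI: 3-29%) at 250 mg/day", and 21% (7-42%) at 375 mg.
- Sections 5.4 and 5.8 give expansion patients 250 mg during RT. Section 14.3.5 sets size, power and evaluability for the 15 new patients and gives no toxicity boundary.
- Section 13.0 lists as a report item "Early stopping rules with supporting data and list the number of participants who have met the early stopping rules". On review frequency it says "During the phase II, the Principal Investigator will review all patient data at least every six months", against at least monthly during escalation.

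**The concern.** DLTs will still be counted in the expansion. Section 7.4 sets the 18-week window without limiting it to escalation, Section 6.2 classes events during RT as DLTs, and the Section 13.0 report gives DLT counts by cohort. No stated numeric decision is attached to those counts, although the report expects early stopping rules to exist.

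The 250 mg estimate comes from a model with only 8 patients at that dose. If the true rate is well above 10%, whether accrual continues depends on individual judgement. Section 14.3.5 also replaces patients with under 4 weeks of DSF with RT. Those who stop early for toxicity would be replaced, so more than 15 could be exposed.

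**Working it through.** **Inputs.** From the documents: initial estimates 0.05/0.10/0.20/0.30; data 1/8 at 250 mg and 2/10 at 375 mg; limit 25%; 15 new patients at 250 mg. Not given: the dose-toxicity model, its prior, which posterior summary the 25% is read on, and whether the two phases would be pooled. Assumed: power model p_k = s_k^a, where s_k is the initial estimate, a = exp(b) and b is normal with mean 0 and SD 1.16 (variance 1.34) or 0.5. The estimate is either the posterior mean of p_k or the plug-in s_k^E(a). A logistic model with intercept 3 or 1 serves as a check. All patients are taken as fully followed.

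**Step 1: the plan's own figures.** With SD 1.16 the plug-in gives 10.4% (2.3-30.0%) at 250 mg and 20.6% (7.2-43.1%) at 375 mg, against the stated 10% (3-29%) and 21% (7-42%). The posterior mean is higher, 12.6% and 22.7%. The plan's figures therefore look like plug-in estimates, but both are carried below.

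**Step 2: what a limit at 125 mg implies at 250 mg.** On one power curve, 25% at 125 mg means a = ln 0.25 / ln 0.05 = 0.463, so 0.10^0.463 = 34% at 250 mg.

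**Step 3: the 125 mg rule, if carried over and pooled.** Add x DLTs among n expansion patients at 250 mg. With SD 1.16 and n = 15 (posterior mean / plug-in):
- x = 9: estimate at 125 mg 24.2% / 23.0%, so no stop.
- x = 10: 26.9% / 25.8%, so stop. The 250 mg estimate is by then 36% / 35%.

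Checked patient by patient (posterior mean), it fires at 7 of 7-8, 8 of 9-11, 9 of 12-14 or 10 of 15, so never before the 7th patient.

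**Step 4: the same 25% limit read at 250 mg.** With SD 1.16 and the posterior mean it trips at 4 of 4-6, 5 of 7-10, 6 of 11-14 or 7 of 15. With SD 0.5 the earliest trip is 5 of 5, and 8 are needed in 15.

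**Step 5: chance of crossing.** Exact sequential binomial: after each patient, the probability at or above the boundary is removed and added up.

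| Power model | 125 mg rule: DLTs in 15 | fires at true 30% | at 40% | 250 mg reading: DLTs in 15 | pause at true 10% | at 20% | at 30% | at 40% |
|---|---|---|---|---|---|---|---|---|
| SD 1.16, mean | 10 | 1.0% | 6.5% | 7 | 0.3% | 6.0% | 25% | 55% |
| SD 1.16, plug-in | 10 | 0.4% | 3.7% | 7 | 0.1% | 3.0% | 17% | 44% |
| SD 0.5, mean | 11 | 0.1% | 1.0% | 8 | <0.1% | 1.4% | 10% | 32% |
| SD 0.5, plug-in | 12 | <0.1% | 0.4% | 8 | <0.1% | 0.9% | 8% | 27% |

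**Step 6: sensitivity.** The logistic model with intercept 3 gives 10 of 15 for the 125 mg rule. With intercept 1 and the posterior mean the boundary is lower: 5 of 5-6, 6 of 7-9, 7 of 10-12, 8 of 13-15. The same recursion then gives about 7% at a true 30% and 25% at 40%. Read at 250 mg under that model, the limit trips at 3 of 3-4, 4 of 5-8, 5 of 9-12 or 6 of 13-15, with a pause chance of about 11% at a true 20%. Expansion data alone, without pooling, would need 5-7 DLTs in 15 for the 125 mg rule.

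**The case against.** The strongest reply is that the rule was never meant for the expansion. A check on the lowest level is the usual safeguard in a continual reassessment design, and it finished its work when escalation closed. That stands. A reader might infer that the rule as written runs through the expansion and fires only after about 10 of 15 DLTs. The phrase allowing the check at any point in the trial permits that reading, but the heading and the 18-patient end point argue against it, and nothing says expansion patients are entered in the program. The count of 10 describes a hypothetical carry-over at full enrolment.

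A reader might also infer that 250 mg already breaches the limit because its interval reaches 29%. The documents do not support that. The 25% limit applies to the posterior estimate, which is 10%. By the same logic 375 mg, with an upper limit of 42%, could not have been declared the MTD.

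Nor is it right that nothing could stop accrual. Section 13.0 provides for ongoing monitoring of serious toxicities and semi-annual QASMC reports, six months is the minimum review frequency, and Section 5.12 lets the cancer center close the study. These safeguards exist but carry no numeric criterion.

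Finally, the proposed rule has limited power. At a true 30% it misses 75-92% of trials under the power-model settings. The table treats each outcome as known before the next enrolment, whereas follow-up lasts 18 weeks. In the most favourable of these settings, crossing by the 10th patient has a chance of only 16.5% at a true 30% and 38.5% at 40%. This stands and limits what the fix can be said to achieve.

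**Conclusion.** The gap is real: on the natural reading no toxicity stopping rule applies to the 15 new patients, and the reporting section presupposes one. Carrying over the 125 mg rule would give little protection. It needs about 10 DLTs in 15 (8-12 across the models, priors and estimators tried, with pooling). Under the power model it cannot fire before about the 7th patient, and it fires in 1% or less of trials at a true 30% and about 0.4-6.5% at 40%. The low-intercept logistic model is less extreme, with firing possible from the 5th patient.

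Reading the existing limit at the expansion dose level gives a modest but real safeguard: 0.3% or less at a true 10%, about 1-6% at 20%, 8-25% at 30% and 27-55% at 40%, somewhat lower in practice because of the 18-week follow-up. All these figures rest on an assumed model and prior. The absence of a stated rule does not. This should be changed, but it does not show that the expansion dose is unsafe.

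**What to change.** In 14.3.5, state that each expansion patient's DLT follow-up is entered in the existing TITE-CRM program with the escalation data, and that accrual pauses for QASMC review if the posterior estimate at the expansion dose level exceeds the plan's existing 25% limit. State the model, prior and estimator, and give the resulting boundary and operating characteristics. Say that anyone evaluable for DLT under 5.9.3 counts, even if replaced under the 4-week criterion in 14.3.5. List the rule in the Section 13.0 report.

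The cost is wording plus re-runs of a program already in use. The downside is a small chance of an unnecessary pause: about 6% or less at true rates up to 20% under the power-model settings, and about 11% at 20% under the low-intercept logistic model. The threshold is the plan's own, and no dose or patient-level rule changes.
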